#### Schema

Prior to discussing protocol entry with the patient, call the Mayo Clinic Cancer Center Registration Office [contact]) to confirm study status and insure that a place on the protocol is currently available to the patient

Cycle length = 21 days

Generic name: Dendritic cells	Generic name: Pneumococcal	Generic name: Pembrolizumab,
Brand name: NA	13-valent Conjugate Vaccine	MK-3475 (anti-PD-1 antibody)
Mayo abbreviation: mDC	(Diphtheria CRM197 Protein)	Brand name: Keytruda®
Availability: Provided through	Brand name: Prevnar13®	Mayo abbreviation: MK-3475
Mayo Clinic Immune,	Mayo abbreviation:	Availability: Commercial supply
Progenitor, and Cell	PREVNAR13	
Therapeutics (IMPACT) Lab	Availability: Provided through	
	Mayo Clinic Pharmacy	

# 1.0 Background

# 1.1 Immune checkpoint blockade responses in advanced melanoma

Melanoma is the most malignant form of skin cancer, and the fifth most common cancer in men and sixth in women in the United States with its highest incidence in the Caucasian population. New cases of melanoma in the USA would reach 73,870 in 2015 and that year, 9,940 patients were expected to die from the disease. Over the last decade, the understanding of the immune checkpoint pathway has paved the way for immunotherapy in metastatic melanoma.

Immune checkpoints are crucial for maintenance of self-tolerance under normal physiological conditions.  However, such maintenance can be dysregulated in tumors as an important mechanism of tumor resistance to immune control. Accumulating evidence shows that antitumor immune responses can be unleashed by immune checkpoint blockade, and blockade of cytotoxic T-lymphocyte antigen 4 (CTLA-4) and programmed death (PD-1) receptor have shown durable anti-melanoma effects.

The PD-1 receptor-ligand interaction is a major pathway used by tumors to suppress immune control. PD-1 receptor (encoded by the gene Pdcd1) is an Ig superfamily member related to CD28 and CTLA-4. It is expressed on the cell surface of activated T-cells under normal conditions. By binding to its ligand (PD-L1 and PD-L2), PD-1 down-regulates T-cell activation and therefore dampens unwarranted and excessive immune responses, including autoimmunity. The interaction between PD-L1 expressed on tumor and stromal cells and PD-1 on T cells can trigger inhibitory signaling pathways that reduce effector cell functions and T-cell-killing capacity. Blocking the PD-1/PD-L1 interaction has been shown to potentiate tumor-specific CD8+ T-cell infiltration and effector T-cell activation that promote tumor rejection.

Anti-PD1/PD-L1 therapy is, to date, one of the most effective single-agent therapies used in the treatment of melanoma, however, it has been shown that as many as 60 % of patients who receive it display primary resistance, and, approximately 25 % of melanoma patients who had objective response to anti-PD1 therapy developed acquired resistance, as characterized by disease progression at a median follow-up of 21 months.

Several studies of advanced melanoma patients suggest that combining therapies that target tumor mechanisms of immune evasion (e.g., removing suppressive cell types via PD1/PD-L1 neutralization) with activation of normal immune cell functionality (i.e. T cell activation) may provide optimal benefits for patients.

# 1.2 Pembrolizumab for advanced melanoma

Pembrolizumab is a human IgG4 PD-1 blocking antibody that is recently approved by the FDA for the treatment of patients with unresectable or metastatic melanoma and disease, including progression following ipilimumab and, if BRAF V600 mutation positive, a BRAF inhibitor. Pembrolizumab showed an unprecedented rate of durable clinical responses, with an overall response rate of 26% and median progression-free survival of 22 weeks (95% CI: 12-36 weeks). Treatment has generally been well-tolerated, and the most common drug-related adverse events (AEs) of any grade were fatigue (33%), pruritus (26%), and rash (18%). Patients responding to treatment showed proliferation of CD8 T cells in their tumors.

Despite the promising data associated with pembrolizumab treatment, the majority of melanoma patients do not respond to pembrolizumab. Several possible mechanisms for pembrolizumab (and other PD-1 blockade) resistance exist, including additional mechanisms of immunosuppression in the tumor microenvironment and derangements in systemic immune competence. The evaluation of melanoma gene expression revealed that tumors infiltrated with CD8+ T cells also

showed expression of a type I interferon transcriptional signature.  Interferon gamma (IFN $\gamma$ ) has the capacity to increase MHC-dependent antigen presentation in a variety of cell populations, including transformed melanocytes both in vitro and in vivo, and is produced in response to T cell recognition of tumor-associated antigens. IFN $\gamma$  also causes many tumor cells to upregulate PD-L1, suggesting that an ongoing T cell response in which IFN $\gamma$  is produced may prime tumors to benefit from anti-PD-1 therapy. Conversely, tumors with few tumor-related T cells have minimal IFN $\gamma$  and are unlikely to benefit from PD-1-based therapies.

The failure of the immune system to recognize and eradicate cancer cells may partly be a result of insufficient immunological activation. One potential hurdle to benefit from anti-PD-1 therapy is a lack expanded tumor-related T cells. As such, there is strong rationale for combining a strategy to expand melanoma-specific tumor-infiltrating lymphocytes (TILs) with pembrolizumab.

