#### 1.34 Safety considerations from DC therapy

DC vaccine therapy clinical trials in melanoma and other types of have thus far demonstrated no significant adverse events or autoimmunity; DC immunotherapy has been used for many different tumors types where adverse events (such as induced autoimmunity) were monitored. Importantly, very few significant adverse effects of DC vaccination have been reported and DC immunotherapy clinical trials performed to date have shown no evidence of resultant generation of auto-immunity. (Table 1). To date, 15 patients with lymphoma, 19 patients with ovarian cancer, and 30 patients with glioblastoma have been treated with DC therapy at Mayo Clinic without any serious drug related toxicity reported. The most common adverse event reported was injection site pain, more often at the time of cryoablation, that usually resolved within 2 days of treatments.

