#### **10.6 Required Routine Reporting**

10.61 Baseline and Adverse Events Evaluations

Pretreatment symptoms/conditions to be graded at baseline and adverse events to be graded at each evaluation.

Grading is per CTCAE v4.0 **unless** alternate grading is indicated in the table below:

CTCAE System Organ Class (SOC)	Adverse event/Symptoms	Baseline	Each evaluation
Blood and lymphatic system disorders	Anemia	Х	Х
Endocrine disorders	Hypothyroidism	Х	Х
Gastrointestinal disorders	Baseline # stools	Х	
	Diarrhea		Х
General disorders	Fatigue	Х	Х
	Fever		Х
	Pain	Х	Х
Immune system disorders	Allergic reaction		Х
	Anaphylaxis		Х
Investigations	Alanine aminotransferase increased	Х	Х
_	Aspartate aminotransferase increased	Х	Х
	Blood bilirubin increased	Х	Х
	Creatinine increased	Х	Х
Metabolism and nutrition disorders	Hyperglycemia	Х	Х
Respiratory, thoracic and mediastinal disorders	Dyspnea	Х	Х
Skin and subcutaneous tissue disorders	Rash, maculo-papular	Х	Х

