10.62 All other AEs

Submit via appropriate MCCC Case Report Forms (i.e., paper or electronic, as applicable) the following AEs experienced by a patient and not specified in Section 10.6:

- 10.621 Grade 2 AEs deemed *possibly*, *probably*, *or definitely* related to the study treatment or procedure.
- 10.622 Grade 3 and 4 AEs regardless of attribution to the study treatment or procedure.

- 10.623 Grade 5 AEs (Deaths)
  - 10.6231 Any death within 30 days of the patient's last study treatment or procedure regardless of attribution to the study treatment or procedure.
    10.6232 Any death more than 30 days after the patient's last study
  - The first study treatment or procedure that is felt to be at least possibly treatment related must also be submitted as a Grade 5 AE, with a CTCAE type and attribution assigned.
- 10.7 Late Occurring Adverse Events

Refer to the instructions in the Forms Packet (or electronic data entry screens, as applicable) regarding the submission of late occurring AEs following completion of the Active Monitoring Phase (i.e., compliance with Test Schedule in Section 4.0).

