15.16 Potential Drug Interactions

There are no known significant drug interactions.

15.17 Known potential toxicities:

Consult the package inset for the most current and complete information.

Common known potential toxicities, >10%: Cardiovascular: Facial edema Central nervous system: Fatigue Dermatologic: Pruritus, skin rash Endocrine & metabolic: Hyperglycemia, hyponatremia, hypoalbuminemia, hypertriglyceridemia, hypocalcemia, decreased sodium bicarbonate Gastrointestinal: Nausea, decreased appetite, constipation, diarrhea, vomiting, abdominal pain Hematologic & oncologic: Anemia, lymphocytopenia Hepatic: Increased serum AST, increased serum ALT, increased serum alkaline phosphatase Neuromuscular & skeletal: Arthralgia Respiratory: Cough, dyspnea Miscellaneous: Fever

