# 16.3 Secondary endpoints

16.31 Safety profile:

All eligible patients that have initiated treatment will be considered evaluable for assessing the safety profile. Toxicities will be graded in terms of severity and relationship to study treatment using CTC-CAE criteria. For each patient who initiated treatment, the maximum grade of each toxicity noted during treatment will be recorded. Frequency tables will be constructed by treatment schedule.

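### The required adverse-event list omits pruritus, so its non-serious Grade 1 cases are not submitted and its any-grade frequency is biased low

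*Combined protocol and SAP*

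**What the plan says.** **Expected events.** Section 1.2 states that "the most common drug-related adverse events (AEs) of any grade were fatigue (33%), pruritus (26%), and rash (18" (the last figure is 18%). Section 15.17, in its group of toxicities above 10%, has the entry "Dermatologic: Pruritus, skin rash". Section 1.34, on earlier dendritic-cell patients at the institution, says: "The most common adverse event reported was injection site pain, more often at the time of cryoablation, that usually resolved within 2 days of treatments".

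**Listed terms.** Section 10.61 introduces its table with "Pretreatment symptoms/conditions to be graded at baseline and adverse events to be graded at each evaluation". The rows for adverse events are anemia, hypothyroidism, diarrhea, fatigue, fever, pain, allergic reaction, anaphylaxis, ALT, AST, bilirubin, creatinine, hyperglycemia, dyspnea and maculo-papular rash. There is no pruritus row and no injection-site row. No minimum grade is set for listed terms.

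**Unlisted terms.** Section 10.62 governs "the following AEs experienced by a patient and not specified in Section 10.6". It asks for Grade 2 events judged at least possibly related, Grade 3 and 4 events whatever their attribution, and Grade 5 events. It does not ask for Grade 1 events.

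**Analysis.** Under Section 16.31, for each treated patient "the maximum grade of each toxicity noted during treatment will be recorded", and frequency tables are made by treatment schedule. The section does not separate terms collected at every grade from terms collected only above a threshold.

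**The concern.** Objective 2.21, the first secondary objective, is the safety profile. Of the three events that Section 1.2 ranks as most common, the required list takes the first, takes the third in one form (maculo-papular rash), and leaves out the second. A site that follows the protocol exactly will submit every Grade 1 case of fatigue and no non-serious Grade 1 case of pruritus. Both terms then appear in the same Section 16.31 tables with nothing to show that one count is complete and the other is cut off below Grade 2.

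At stake is the reading of those tables. The total for pruritus could not be compared with the total for fatigue beside it, or with the 26% that the protocol itself cites for pembrolizumab. With no baseline row, itch already present at entry would not be recorded through this table either.

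**Working it through.** **1. The plan's own figure.** The plan states no expected adverse-event frequency for this trial, so there is none to reproduce. The figure that fixes the denominator is the sample size in Section 16.2: 33 patients, null 12%, alternative 30%, one-sided exact binomial test at 0.10, 90% power. The smallest rejection threshold with exact size at or below 0.10 is 7 responses: P(X >= 7 | 33, 0.12) = 0.0930 and P(X >= 7 | 33, 0.30) = 0.9056. The stated power reproduces. Nothing below depends on it.

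**2. What is collected, by grade.**

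| Event | Listed in 10.61? | Grade 1, non-serious | Grade 2, related | Grade 3-5 |
|---|---|---|---|---|
| Fatigue | Yes | Submitted | Submitted | Submitted |
| Rash, maculo-papular | Yes | Submitted | Submitted | Submitted |
| Pain (any site) | Yes | Submitted | Submitted | Submitted |
| Pruritus | No | Not submitted | Submitted | Submitted (Grade 5 within 30 days of treatment, or later if possibly related) |

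**3. Size for pruritus.** Inputs:
- any-grade rate 26% (Section 1.2), taken as an assumption to apply to this population;
- n = 33, or at most 39 over both schedules (Section 16.2);
- s, the share of patients with pruritus whose worst grade is 1. The documents do not give s.

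Expected patients with pruritus: 33 x 0.26 = 8.6, or 39 x 0.26 = 10.1.

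Reported rate = 26% x (1 - s). Reported count = n x 0.26 x (1 - s).

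| Assumed s | Reported rate | Reported patients of 33 | Reported patients of 39 |
|---|---|---|---|
| 25% | 19.5% | 6.4 | 7.6 |
| 50% | 13.0% | 4.3 | 5.1 |
| 75% | 6.5% | 2.1 | 2.5 |
| 90% | 2.6% | 0.9 | 1.0 |

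The direction does not depend on s: any share above zero biases the rate low.

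**4. Is pruritus alone?** No. Section 15.17 also puts nausea, arthralgia, cough, constipation, vomiting and decreased appetite above 10%. None has a row in table 10.61, so each is cut off in the same way. Pruritus stands out because Section 1.2 gives it a rate and a rank.

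**5. Injection site.** The local event that Section 1.34 names is pain. Pain has a row in table 10.61 at baseline and at each evaluation, so Grade 1 cases are collected. What is lost is the separation from tumor pain.

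**The case against.** The strongest reply is that this is an openly stated collection rule, not a mistake. A short required list with a grade threshold for everything else is consistent within itself, and Section 16.31 speaks only of toxicities noted during treatment. It promises neither any-grade totals nor a comparison with Section 1.2. That much stands: no section contradicts another, and the point concerns a design choice.

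It also stands that adding one row leaves the other unlisted terms above 10% cut off, so the labelling of the tables carries the general remedy. And no decision rests on Grade 1 events. Both definitions of dose-limiting toxicity (Sections 7.0 and 16.1) need Grade 3 or higher, or specified Grade 2 events that do not resolve. Section 16.13 counts treatment-related deaths, Grade 4 hematologic and Grade 3 or worse non-hematologic toxicity, and the safety checks in Section 16.5 count dose-limiting toxicities.

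Four stronger readings are tempting and are not supported:
- *Grade 1 pruritus can never reach the database.* Section 10.1 sends expedited reports through routine reporting as well, so a serious Grade 1 event would arrive. The Case Report Form packet (Section 18.1) is not among the documents, so the forms may ask for more than the protocol does.
- *The table will rank rash above pruritus, reversing Section 1.2.* At 18% and 26% this needs s above 1 - 18/26 = 31%. At s = 25%, pruritus is still ahead, 19.5% to 18%. Rash is also collected in full only if it is maculo-papular; Section 1.2 says only rash.
- *Grade 1 injection-site pain is lost.* It can be recorded under Pain, with a baseline grade and an attribution to agent or procedure (Section 10.3) that partly separate it from tumor pain. Section 1.34 does not report other injection-site reactions as common.
- *The trial will see 26% pruritus.* That is a background rate. Section 3.13 requires earlier PD-1 or PD-L1 treatment, and Section 3.29b excludes patients not recovered to Grade 1 or less, so the rate here may differ.

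**Conclusion.** The point holds as a limited gap in a secondary safety description, worth correcting because the correction is cheap. Under the written rule, non-serious Grade 1 pruritus is not submitted, so its any-grade frequency in the Section 16.31 tables is biased low. For s between 25% and 90%, 26% would appear as 19.5% down to 2.6%. Those figures rest on two assumptions: the range of s, which no document supplies, and the transfer of the background 26% to pretreated patients. The downward direction needs neither; it needs only that some patients have pruritus no worse than Grade 1 and that the forms follow Section 10.62.

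The same cut-off applies to other unlisted common terms. Sample size, alpha, power, dose-limiting toxicities, stopping rules, Grade 3 or higher data and the primary endpoint are untouched.

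**What to change.** - In table 10.61, add a Pruritus row, graded at baseline and at each evaluation. An injection-site reaction row is optional; its use would be to separate local reactions from tumor pain.
- In Section 16.31, report any-grade frequencies only for terms listed in table 10.61. Report every other term as related Grade 2 and as Grade 3 or higher, and label the tables so that a reader can see which rule applies to each term. This also covers nausea, arthralgia, cough and the other unlisted terms without lengthening the form.

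The cost is one extra line on the adverse-event form, a short addition to Section 16.31, and slightly more data entry per visit. Grade 1 events not collected so far may not be recoverable, but the labelling can be applied at any stage.

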# **1.3** Evidence for dendritic cell vaccine immunotherapy in cancer.

Dendritic cells (DCs) are the professional antigen-presenting cells that induce and regulate both adaptive and innate immune responses. DCs have been used in the past by exposing these cells to some form of tumor antigen *in vitro*, and then returning antigen-loaded DCs to the patient to stimulate anti-tumor immunity. Clinical trials of DC immunotherapy have suggested that this approach can result in significant stimulation of the immune response against many different forms of cancer.

The use of DCs as vaccines showed beneficial effects in an autologous setting and led to the first FDA approved immunotherapy. DC immunotherapy consists of exposing dendritic cells to tumor antigen and using the antigen-loaded DCs as a vaccine to stimulate anti-tumor response.

Since 1996, there have been several clinical studies investigating tumor antigen-loaded DC-based vaccines, mainly in metastatic melanoma patients.  Over the years, many parameters in DC vaccination have been optimized in clinical studies; DC vaccination has only minimal side effects and thus provides a well-tolerable treatment. 

# 1.31 Dendritic Cell generation for vaccine therapy

Results of this immunotherapy method against many different forms of cancer have been encouraging in animal models but have had mixed results in clinical trials  Available evidence suggests that the quality of the DC preparation used in a vaccination protocol has a substantial impact on the immune response elicited.  Specifically, the functional status of DCs depends on their state of activation at the time they are delivered, completely activated DC (mature DCs or mDCs) are able to migrate to lymph nodes and initiate stimulation of the immune system *in vivo*, while immature DCs can inhibit effector T cell function and induce tolerance. Unfortunately, many clinical trials were initiated before this distinction came to light and patients received immature DCs; inhibiting the immune response instead of stimulating it.  Thus, the lack of potent immune stimulation and unsatisfactory clinical response demonstrated in earlier trials of DC immunotherapy may at least in part be attributable to the functional state of the DCs employed. 

#### 1.32 Ex vivo-generated DC vaccines.

DCs that are generated *ex vivo* by culturing hematopoietic progenitor cells or monocytes with cytokine combinations have been tested as therapeutic vaccines in cancer patients for more than a

decade.  Treatment of metastatic prostate cancer with sipuleucel-T (also known as APC 8015), approved by the US Food and Drug Administration (FDA) for the treatment of metastatic prostate cancer, consists of a cellular product based on enriched blood antigen-presenting cells (APCs) that are briefly cultured with a fusion protein of prostatic acid phosphatase (PAP) and GM-CSF; this resulted in an approximately 4-month-prolonged median survival in Phase III trials. 

A Phase III trial in metastatic melanoma that tested peptide vaccine in combination with highdose IL-2 versus IL-2 alone showed significant improvement in overall response rate and progression-free survival in patients who received the vaccine. Also, a Phase III trial in patients with follicular lymphoma (FL) showed that an idiotype vaccine therapy significantly prolongs the duration of chemotherapy-induced remission  (Table 1).

Vaccine and antigen	Indication	Key observations	Refs
GM-CSF-IL-4 DCs with or without	Metastatic prostate	One of the first studies that tested the	45
HLA-A*0201-restricted peptides or	cancer	immunogenicity of DCs	
peptides alone			
GM-CSF-IL-4 DCs with peptides,	Stage IV melanoma,	
 
Loading DCs with complex antigen
 
	46-48
tumour lysates or autologous tumour-	renal cell carcinoma	preparations	
eluted peptides	and malignant glioma	Objective clinical responses	
Blood DCs and idiotype antigens	Multiple myeloma	Immunogenicity of DCs	49,50
		Tumour regression	
Mature GM-CSF-IL-4 DCs and	Stage IV melanoma	Well-controlled and validated vaccine	51
peptides	e	manufacture process	
		Testing mature DCs	
		Immunogenicity	
		Objective clinical responses	
CD34 + HPC-derived DCs and peptides	Stage IV melanoma	• One of the first studies to test CD34 +	52,53
	Suger in menune	HPC-derived DCs	
		• Loading vaccines with a mixture of well-	
		defined peptides	
		• Durable immune responses in long-term	
		survivors	
		Objective clinical responses	
FLT3 ligand-expanded blood DCs and	Advanced CEA +	Immunogenicity	54
altered peptides	cancer	Objective clinical responses	-
Immature GM-CSF–IL-4 DCs	Healthy volunteers	Antigen-specific inhibition of effector T	40
miniature GWI-EBI 11-4 DE3	Treating volunteers	cell function after injection of immature	
		DCs	
GM-CSF-IL-4 DCs and tumour lysates	Refractory pediatric	Immunogenicity	55
GWI-CSI-IL-4 DCs and tuniour tysates	solid tumors	Objective clinical responses	
Mature cryopreserved GM-CSF-IL-4	Stage IV melanoma	Immunogenicity	56
DCs	Stage IV metanoma	minunogementy	50
DCs loaded with autologous tumour	Colon cancer	Feasibility	57
RNA		Immunogenicity	
DCs loaded with killed allogeneic	Stage IV melanoma	Immunogenicity	58,59
tumour cells	2	Durable objective clinical responses	
		• Long-term survival	
Monocyte-derived DCs loaded with the	Advanced cancer	Adjuvant effect of NK cell activation on	60
NK T cell ligand $\alpha$ -galactosylceramide		$CD8^+$ T cell-mediated immune response	
Monocyte-derived DCs	Melanoma	In vivo identification of antigen-specific	61
	10101ullollu	immune response by PET imaging in	
		patients	
		Route of DC administration affects T cell	62
		activation, with intra-dermal	
		administration showing better responses	
		than intra-nodal administration	
	 	man mua-noual aummisuation	I

Table 1 Examples of clinical trials testing vaccination with ex vivo DCs 

Vaccine and antigen	Indication	Key observations	Refs
Comparative study of CD34 + HPC-	Melanoma	Langerhans cell-based vaccines stimulated	63
derived Langerhans cells versus		significantly greater tyrosinase-HLA-	
monocyte-derived DCs		A*0201 tetramer reactivity than the	
		monocyte-derived DC vaccines	
Type 1-polarized monocyte-derived	Glioma	Combination of DC vaccination with	64
DCs		polyICLC to trigger systemic	
		inflammation driven by type I interferon	
		family members	
CEA, carcinoembryonic antigen; DC, de	endritic cell; IL-4, int	erleukin-4; GM-CSF, granulocyte-macrophage colo	ony-
stimulating factor; HLA, human leukoc	yte antigen; HPC, hae	ematopoietic progenitor cell; NK cell, natural killer c	ell;
PET, positron emission tomography; po	lyICLC, polyinosinic	-polycytidylic acid stabilized with poly-L-lysine an	d
carboxymethylcellulose.			

